Appendix 1. Abbreviations

Abbreviation	Term
ADA	Anti-drug Antibody
ADC	Anti-Drug Congugate
AE	Adverse Event
ALT	Alanine Aminotransferase
AST	Aspartate Aminotransferase
AUC	Area Under the Curve
BP	Blood Pressure
C1D1	Cycle 1 Day 1
CBC	Complete Blood Count
CLX	Cell Line Xenograft
CNS	Central Nervous System
CR	Complete Response
CRF	Case Report Form
CT	Computed Tomography
CTC	Circulating Tumor Cells
CTCAE	Common Terminology Criteria for Adverse Events
DAI	Dosage Administration Instruction
DFS	Disease Free Survival
DLT	Dose Limiting Toxicities
ECG	Electrocardiograms
ECOG	Eastern Cooperative Oncology Group
HNSTD	Highest Non-Severely Toxic Dose
ICH	International Conference on Harmonisation
IHC	Immunohistochemistry
IND	Investigational New Drug
ITT	Intent-to-Treat
IV	Intravenous
mg/kg	Milligram/kilogram
mITT	Modified Intent-to-Treat
MRI	Magnetic Resonance Imaging
MTD	Maximum Tolerated Dose
mTPI	Modified Toxicity Probability Interval
N/A	Not Applicable
NCI	National Cancer Institute
ORR	Overall Response Rate
OS	Overall Survival
PD	Progressive Disease
PDX	Patient Derived Xenograft
PK	Pharmacokinetic
PFS	Progression Free Survival
PR	Partial Response

PR	Pulse Rate
RECIST	Response Evaluation Criteria in Solid Tumors
RP2D	Recommended Phase 2 Dose
SAE	Serious Adverse Event
SD	Stable Disease
TNBC	Triple Negative Breast Cancer
ULN	Upper Limit of Normal
US	United States
WBC	White Blood Cell

Appendix 2. RECIST (Response Evaluation Criteria In Solid Tumors) version 1.1 Guidelines

Adapted from E.A. Eisenhauer, et al: New response evaluation criteria in solid tumours: Revised RECIST guideline (version 1.1). European Journal of Cancer 45 (2009) 228–247.

CATEGORIZING LESIONS AT BASELINE

Measurable Lesions

Lesions that can be accurately measured in at least one dimension.

- Lesions with longest diameter twice the slice thickness and at least 10 mm or greater when assessed by CT or MRI (slice thickness 5-8 mm).
- Lesions with longest diameter at least 20 mm when assessed by Chest X-ray.
- Superficial lesions with longest diameter 10 mm or greater when assessed by caliper.
- Malignant lymph nodes with the short axis 15 mm or greater when assessed by CT.

NOTE: The shortest axis is used as the diameter for malignant lymph nodes, longest axis for all other measurable lesions.

Non-measurable disease

Non-measurable disease includes lesions too small to be considered measurable (including nodes with short axis between 10 and 14.9 mm) and truly non-measurable disease such as pleural or pericardial effusions, ascites, inflammatory breast disease, leptomeningeal disease, lymphangitic involvement of skin or lung, clinical lesions that cannot be accurately measured with calipers, abdominal masses identified by physical exam that are not measurable by reproducible imaging techniques.

- Bone disease: Bone disease is non-measurable with the exception of soft tissue components that can be evaluated by CT or MRI and meet the definition of measurability at baseline.
- Previous local treatment: A previously irradiated lesion (or lesion patiented to other local treatment) is non-measurable unless it has progressed since completion of treatment.

Normal sites

- Cystic lesions: Simple cysts should not be considered as malignant lesions and should not be recorded either as target or non-target disease. Cystic lesions thought to represent cystic metastases can be measurable lesions, if they meet the specific definition above. If non-cystic lesions are also present, these are preferred as target lesions.

- Normal nodes: Nodes with short axis <10 mm are considered normal and should not be recorded or followed either as measurable or non-measurable disease.

Recording Tumor Assessments

All sites of disease must be assessed at baseline. Baseline assessments should be done as close as possible prior to study start. For an adequate baseline assessment, all required scans must be done within 28 days prior to treatment and all disease must be documented appropriately. If baseline assessment is inadequate, subsequent statuses generally should be indeterminate.

Note: For the patient population being evaluated in this protocol, the baseline assessment may be completed within 6 weeks prior to randomization.

Target lesions

All measurable lesions up to a maximum of 2 lesions per organ, 5 lesions in total, representative of all involved organs, should be identified as target lesions at baseline. Target lesions should be selected on the basis of size (longest lesions) and suitability for accurate repeated measurements. Record the longest diameter for each lesion, except in the case of pathological lymph nodes for which the short axis should be recorded. The sum of the diameters (longest for non-nodal lesions, short axis for nodal lesions) for all target lesions at baseline will be the basis for comparison to assessments performed on study.

- If two target lesions coalesce the measurement of the coalesced mass is used. If a large target lesion splits, the sum of the parts is used.
- Measurements for target lesions that become small should continue to be recorded. If a target lesion becomes too small to measure, 0 mm should be recorded if the lesion is considered to have disappeared; otherwise a default value of 5 mm should be recorded.

NOTE: When nodal lesions decrease to <10 mm (normal), the actual measurement should still be recorded.

Non-target disease

All non-measurable disease is non-target. All measurable lesions not identified as target lesions are also included as non-target disease. Measurements are not required but rather assessments will be expressed as ABSENT, INDETERMINATE, PRESENT/NOT INCREASED, INCREASED. Multiple non-target lesions in one organ may be recorded as a single item on the case report form (eg, 'multiple enlarged pelvic lymph nodes' or 'multiple liver metastases').

OBJECTIVE RESPONSE STATUS AT EACH EVALUATION

Disease sites must be assessed using the same technique as baseline, including consistent administration of contrast and timing of scanning. If a change needs to be made the case must be discussed with the radiologist to determine if substitution is possible. If not, subsequent objective statuses are indeterminate.

Target disease

- Complete Response (CR): Complete disappearance of all target lesions with the exception of nodal disease. All target nodes must decrease to normal size (short axis <10 mm). All target lesions must be assessed.
- Partial Response (PR): Greater than or equal to 30% decrease under baseline of the sum of diameters of all target measurable lesions. The short diameter is used in the sum for target nodes, while the longest diameter is used in the sum for all other target lesions. All target lesions must be assessed.
- Stable: Does not qualify for CR, PR or Progression. All target lesions must be assessed. Stable can follow PR only in the rare case that the sum increases by less than 20% from the nadir, but enough that a previously documented 30% decrease no longer holds.
- Objective Progression (PD): 20% increase in the sum of diameters of target measurable lesions above the smallest sum observed (over baseline if no decrease in the sum is observed during therapy), with a minimum absolute increase of 5 mm.
- Indeterminate. Progression has not been documented, and
 - one or more target measurable lesions have not been assessed;
 - or assessment methods used were inconsistent with those used at baseline;
 - or one or more target lesions cannot be measured accurately (eg, poorly visible unless due to being too small to measure);
 - or one or more target lesions were excised or irradiated and have not reappeared or increased.

Non-target disease

- CR: Disappearance of all non-target lesions and normalization of tumor marker levels. All lymph nodes must be 'normal' in size (<10 mm short axis).
- Non-CR/Non-PD: Persistence of any non-target lesions and/or tumor marker level above the normal limits.

- PD: Unequivocal progression of pre-existing lesions. Generally the overall tumor burden must increase sufficiently to merit discontinuation of therapy. In the presence of SD or PR in target disease, progression due to unequivocal increase in non-target disease should be rare.
- Indeterminate: Progression has not been determined and one or more non-target sites were not assessed or assessment methods were inconsistent with those used at baseline.

New Lesions

The appearance of any new unequivocal malignant lesion indicates PD. If a new lesion is equivocal, for example due to its small size, continued assessment will clarify the etiology. If repeat assessments confirm the lesion, then progression should be recorded on the date of the initial assessment. A lesion identified in an area not previously scanned will be considered a new lesion.

Supplemental Investigations

- If CR determination depends on a residual lesion that decreased in size but did not disappear completely, it is recommended the residual lesion be investigated with biopsy or fine needle aspirate. If no disease is identified, objective status is CR.
- If progression determination depends on a lesion with an increase possibly due to necrosis, the lesion may be investigated with biopsy or fine needle aspirate to clarify status.

Patientive progression

Patients requiring discontinuation of treatment without objective evidence of disease progression should not be reported as PD on tumor assessment CRFs. This should be indicated on the end of treatment CRF as off treatment due to Global Deterioration of Health Status. Every effort should be made to document objective progression even after discontinuation of treatment.

Table 1. Objective Response Status at each Evaluation

Target Lesions	Non-target Disease	New Lesions	Objective status
CR	CR	No	CR
CR	Non-CR/Non-PD	No	PR
CR	Indeterminate or Missing	No	PR
PR	Non-CR/Non-PD, Indeterminate, or Missing	No	PR
SD	Non-CR/Non-PD, Indeterminate, or Missing	No	Stable
Indeterminate or Missing	Non-PD	No	Indeterminate
PD	Any	Yes or No	PD
Any	PD	Yes or No	PD
Any	Any	Yes	PD

Table 2. Objective Response Status at each Evaluation for Patients with Non-Target Disease Only

Non-target Disease	New Lesions	Objective status
CR	No	CR
Non-CR/Non-PD	No	Non-CR/Non-PD
Indeterminate	No	Indeterminate
Unequivocal progression	Yes or No	PD
Any	Yes	PD

Appendix 3. ECOG Performance Status

Grade	ECOG Performance Status
0	Fully active, able to carry on all pre-disease performance without restriction.
1	Restricted in physically strenuous activity but ambulatory and able to carry out work of a light or sedentary nature, eg, light house work, office work.
2	Ambulatory and capable of all self-care but unable to carry out any work activities. Up and about more than 50% of waking hours.
3	Capable of only limited self-care, confined to bed or chair more than 50% of waking hours.
4	Completely disabled. Cannot carry on any self-care. Totally confined to bed or chair.
5	Dead.

*As published in Am J Clin Oncol 5:649-655, 1982.

Appendix 4. National Cancer Institute (NCI) Common Terminology Criteria for Adverse Events (CTCAE)

The NCI CTCAE (Version 4.03 dated June 14, 2010) has been placed in the Study Manual for this protocol. Alternatively, the NCI CTCAE may be reviewed on-line at the following NCI website: <http://ctep.cancer.gov/reporting.ctc.html>

Appendix 5. Management of Infusion Related Reactions Including Allergic Reactions, Cytokine Release Syndrome or Anaphylaxis

In the event of infusion related reactions, Investigators should institute treatment measures according to best medical and nursing practice.

The following treatment guidelines should be employed:

If chills and fever occur, the infusion should be interrupted. Patients may be treated symptomatically and the infusion should be restarted at 50% of the original rate.

NCI-CTCAE Grade 1 allergic reaction or cytokine release syndrome

- Monitor for worsening condition. If the reaction worsens, stop the infusion. Institute premedication for subsequent infusions as per Section [Administration](#).

NCI-CTCAE Grade 2 allergic reaction or cytokine release syndrome

- Stop PF-06647263 infusion.
- Administer bronchodilators, oxygen, acetaminophen, and others as medically indicated.
- Resume infusion at 50% of previous rate once reaction has decreased to \leq Grade 1 in severity. Monitor closely for any worsening including respiratory status. If the reaction recurs, stop infusion. Institute premedication for subsequent infusions as per Section [Administration](#).

NCI-CTCAE Grade 3 or Grade 4 allergic reaction or cytokine release syndrome or anaphylaxis

- A Grade 3 anaphylaxis (hypersensitivity reaction) consists of symptomatic bronchospasm requiring parenteral medications with or without urticaria, allergy-related edema/angioedema, or hypotension.
- A Grade 4 anaphylaxis (hypersensitivity reaction) is a life-threatening event requiring urgent intervention.

Treatment of Grade 3 or Grade 4 allergic reaction, cytokine release syndrome or anaphylaxis

- Stop the PF-06647263 infusion immediately and disconnect infusion tubing from the patient.
- Administer epinephrine, bronchodilators, antihistamines, glucocorticoids, intravenous fluids, vasopressor agents, oxygen, and others as medically indicated.

- Monitor closely respiratory and cardiovascular status, be prepared for potential need for intubation.
- Telephone Sponsor or designated representative to report an SAE as per Section [Adverse Event Reporting](#).
- For a NCI-CTCAE Grade 3 or 4 hypersensitivity reaction, study treatment will be discontinued.

Re-treatment following Grade 1 or Grade 2 allergic reactions or cytokine release syndrome

- Once the PF-06647263 infusion rate has been decreased due to an allergic reaction or cytokine release syndrome, it will remain decreased for all subsequent infusions.
- If the patient has a second reaction at the lower infusion rate, the infusion should be stopped and the patient should receive no further PF-06647263.
- If the patient experiences a Grade 3 or 4 allergic reaction, cytokine release syndrome, or anaphylaxis at any time, the patient should receive no further PF-06647263.
- If there are questions concerning whether an observed reaction is consistent with an allergic reaction, cytokine release syndrome, or anaphylaxis, the medical monitor should be contacted immediately to assist with grading the reaction.
- PK, PD and ADA sampling should continue as long as the sampling does not interfere with the medical treatment of the patient.

PF-06650808

B7501001

Final Protocol Amendment 1, 07May 2014

CCI

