5.2.6. Dose Reductions

Dose reductions or delays in the administration of PF-06650808 are permitted as described below for PF-06650808 related toxicity. The sponsor should be notified when dose reductions are planned and consulted for any dose reduction related questions.

Once a dose has been reduced for a given patient, all subsequent cycles should be administered at that dose level, unless further dose reduction is required. The reduced dose will be considered the maximum dose for all subsequent cycles for that patient. Doses should be reduced to the next lowest cohort dose level. Dose re-escalation is not allowed.

Patients enrolled in the first cohort should be discontinued from the study if more than 1 dose reduction is required. Patients enrolled in subsequent cohorts should be discontinued from the study if more than 2 dose reductions are required. For patients experiencing an adverse

event related to PF-06650808 that fails to recover to CTCAE Grade 1 (or within 1 grade of starting values for pre-existing laboratory abnormalities) leading to treatment delay of >2 weeks should be discontinued unless discussed with the sponsor.

The following table summarizes the actions following the toxicities observed during the study period.

Event	Action
Grade 3 or 4 nonhematologic toxicity considered at least possibly related to PF-06650808 per investigator judgment (including persistent nausea, vomiting, diarrhea despite optimal medical therapy)	
 Hold PF-06650808 infusion until recovery to Grade 0-1 or baseline and reduce by 1 dose level. Discontinue PF-06650808 if dose delay is more than 2 weeks. If toxicity reoccurs despite reduction, patient may be dose reduced again by another dose level upon recovery to grade 0-1 or baseline unless the patient is in the first dose group, then only 1 dose reduction is allowed. Prompt palliative measures are strongly encouraged (eg, anti-emetics). Patients who experience Grade 4 non hematologic toxicities despite intervention should be discontinued from the study.

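### Protocol 5.2.6 tells sites to hold and dose-reduce after a related Grade 3 infusion reaction for which Appendix 5 bars further drug; Appendix 5 also carries a wrong drug code and an ambiguous Grade 2 instruction

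*Protocol*

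**What the plan says.** **Section 5.2.6.** The table row for Grade 3 or 4 nonhematologic toxicity judged at least possibly related to study drug instructs: "Hold PF-06650808 infusion until recovery to Grade 0-1 or baseline and reduce by 1 dose level". If the toxicity returns, a second reduction is allowed, except in the first dose group. Grade 4 toxicity that occurs despite intervention leads to discontinuation. The row neither excepts infusion reactions nor refers to Appendix 5.

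**Appendix 5, Grade 3 or 4 reactions.** Acute management begins: "Stop the PF-06647263 infusion immediately and disconnect infusion tubing from the patient". The same list ends: "For a NCI-CTCAE Grade 3 or 4 hypersensitivity reaction, study treatment will be discontinued". The re-treatment section adds, for a Grade 3 or 4 allergic reaction, "cytokine release syndrome, or anaphylaxis at any time, the patient should receive no further PF-06647263".

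**Appendix 5, Grade 2 reactions.** The first step is "Stop PF-06647263 infusion". After recovery the infusion restarts at half rate, and then: "If the reaction recurs, stop infusion. Institute premedication for subsequent infusions as per Section" on administration. For a second reaction at the lower rate, the re-treatment section says "the infusion should be stopped and the patient should receive no further PF-06647263".

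**Sections 5.2.3 and 3.3.** Section 5.2.3 calls for premedication before later infusions, with a parenthesis limiting this to patients who can continue under Appendix 5. Section 3.3 excludes Grade 3 or higher reactions of this kind from the DLTs, says they may justify discontinuation, and asks for review with the sponsor.

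**The concern.** Dose-modification tables are what site staff use when deciding whether and how to give the next infusion. If the table gives a reduced-dose path for an event that an appendix treats as a permanent stop, the decision depends on which page is consulted. Here the events are severe allergic reaction, cytokine release syndrome and anaphylaxis, in an early dose-escalation study of an antibody-drug conjugate. What is at stake is the safety of an individual patient at re-exposure, not any estimate or error rate.

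The drug code raises a related doubt. Text carrying another compound's number may have been taken from another protocol, although the documents do not say so. The sponsor should confirm that the guidance was meant for this drug.

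**Working it through.** No sample size, power or event figure is involved, so the check is a comparison of texts and a count.

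**1. The rules side by side**

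| Situation | 5.2.6 table | Appendix 5 | Relation |
|---|---|---|---|
| Related Grade 3 allergic reaction, cytokine release syndrome or anaphylaxis | Hold, restart one level lower; a further reduction is possible | No further drug | Conflict |
| The same reactions at Grade 4 | Hold and reduce, but discontinue if Grade 4 despite intervention | No further drug | Conflict only where 5.2.6 would not already discontinue |
| Second reaction at the lower rate (heading covers Grade 1 or 2 reactions) | Outside the Grade 3 or 4 row | No further drug | No conflict with that row |

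The first two rows assume that these reactions count as nonhematologic. Nothing in the hematologic rows of 5.2.6 describes them.

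**2. Could the 5.2.6 path be followed in practice?** Yes. Section 5.2.5 lets a new cycle start once nonhematologic toxicity has returned to baseline or Grade 1 or lower, with blood counts adequate. A reaction that resolves before the next dosing day meets the nonhematologic condition, so the section gives no separate barrier.

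**3. Does the conflict depend on the drug code?** No. The stop for Grade 3 or 4 hypersensitivity names no code, and correcting the code elsewhere leaves 5.2.6 unchanged.

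**4. Count of PF-06647263**
- Acute management: the Grade 2 stop, and the Grade 3 or 4 stop = 2.
- Re-treatment: reduced rate kept, no drug after a second reaction, no drug after Grade 3 or 4 = 3.
- Total 2 + 3 = 5. The code appears nowhere else in the supplied text.
- Appendix 5 instructions naming PF-06650808: 0. That code appears there only in a page label.

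Section 2.1 defines PF-06650808, PF-06460005 and PF-06380101, and Section 3.1 describes a single-agent study.

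**5. The Grade 2 bullet.** Two readings are open. In one, premedication is for patients whose reaction did not recur, which agrees with the re-treatment section. In the other, the sentences are taken in order, so a patient whose reaction recurred is premedicated for later infusions, which the re-treatment section forbids. The Grade 1 bullet has the same order (stop, then premedicate), and stopping there evidently does not end treatment. The second reading is therefore one that a site could reasonably adopt.

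**The case against.** The best defence is that the specific rule governs the general one. Section 5.2.3 already hands the question of continuing after an infusion reaction to Appendix 5, and Appendix 5 applies its Grade 3 or 4 bar at any time. Section 5.2.4 presents the modifications as recommended, and 5.2.6 describes reductions as permitted. Re-exposure would also have to pass several sponsor contacts: review under 3.3, notification of infusion reactions under 5.2.3, notification of planned reductions under 5.2.6, and the Appendix 5 instruction "Telephone Sponsor or designated representative to report an SAE as per Section" on adverse event reporting. Doubts about grading go to the medical monitor.

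Much of this stands. It makes Appendix 5 the likely intention and lowers the chance of harm. It does not remove the contradiction: the 5.2.3 pointer is a parenthesis about premedication that sets no precedence, the 5.2.6 action is worded as an instruction, and sponsor contact is a safeguard rather than a rule.

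Four stronger readings are tempting, and the documents do not support them:

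- *Every no-further-drug rule in Appendix 5 conflicts with 5.2.6.* The second-reaction rule concerns patients re-treated after Grade 1 or 2 reactions, whom the Grade 3 or 4 row does not reach.
- *The Grade 2 bullet contradicts the re-treatment section.* The bullet never says that treatment continues after a recurrence at half rate. It is ambiguous.
- *Two reduced-dose re-treatments are allowed where Appendix 5 allows none.* The limit of two reductions (one in the first cohort) applies only if 5.2.6 is read alone. It is not an expected consequence of the protocol as a whole.
- *The wrong code leaves patients without a stopping rule.* Only one drug is given, 5.2.3 ties Appendix 5 to it, and the hypersensitivity stop names no code. That stop closes a list headed for all three reaction types, so it may also be read as covering cytokine release syndrome.

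**Conclusion.** The concern holds as a conflict between 5.2.6 and Appendix 5 over related Grade 3 allergic reaction, cytokine release syndrome and anaphylaxis. For Grade 4 it is partial. Appendix 5 is probably the intended rule, but 5.2.6 contains neither an exception nor a cross-reference.

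The undefined code in five instructions is certain but close to clerical. The Grade 2 wording is an ambiguity that merits clarification. The count rests on the supplied text; removed pages and redactions could not be searched.

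The point is a patient-safety correction worth making. Sample size, the 25% DLT target and the planned analyses stay as they are.

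**What to change.** 1. In the Grade 3 or 4 nonhematologic row of the 5.2.6 table, add: *Exception: for Grade 3 or 4 allergic reaction, cytokine release syndrome or anaphylaxis, Appendix 5 governs; permanently discontinue PF-06650808.*
2. Confirm that the Appendix 5 guidance applies to this drug, then replace PF-06647263 with PF-06650808 in all five places.
3. As a clarification only, state in the Grade 2 bullet that premedication for later infusions applies if the reaction does not recur at the reduced rate.

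The cost is a text amendment: one exception, five code replacements and one clarified bullet. Replacing the code alone would leave items 1 and 3 open.

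### Protocol Appendix 5 gives two outcomes when a Grade 2 infusion reaction recurs at the halved rate: premedicate later infusions, or no further dosing at all

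*Protocol*

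**What the plan says.** All the conflicting text is in Protocol Appendix 5 (management of infusion related reactions).

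- **Grade 2 bullet.** The infusion is stopped, then: "Resume infusion at 50% of previous rate once reaction has decreased to" Grade 1 or less. For what follows, the bullet says: "If the reaction recurs, stop infusion. Institute premedication for subsequent infusions", with a pointer to the Administration section (5.2.3).
- **Re-treatment bullets**, headed "Re-treatment following Grade 1 or Grade 2 allergic reactions or cytokine release syndrome". A rate that was lowered because of an allergic reaction or cytokine release syndrome is not raised again: "it will remain decreased for all subsequent infusions". Then: "If the patient has a second reaction at the lower infusion rate, the infusion should be stopped and the patient should receive no further" drug.
- **General sentence ahead of the graded bullets.** "If chills and fever occur, the infusion should be interrupted", and it is restarted at 50% of the original rate.
- **Grade 1 bullet.** "Monitor for worsening condition. If the reaction worsens, stop the infusion". It ends with the same premedication sentence as the Grade 2 bullet.

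Section 5.2.3 describes infusion related reactions as marked by fever and chills and, less often, hypotension. It asks for premedication before subsequent infusions only where Appendix 5 allows the patient to continue.

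**The concern.** A reaction that returns after the infusion has been resumed at half rate is, literally, a second reaction at the lower rate. The Grade 2 bullet then foresees later infusions with premedication, and the re-treatment bullet forbids them. An investigator following either one is following the protocol.

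This is a stopping and rechallenge rule, so what is at stake first is which patients are exposed again after two reactions. The study is planned for approximately 3-4 sites, and if they read the appendix differently, discontinuations for infusion reactions and the number of cycles received will partly reflect the reading and not the drug.

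**Working it through.** No formula applies to the main point, and the plan has no figure to reproduce. The check is to follow one patient through both instructions. Appendix 5 uses a compound code other than the study drug's; that is a separate matter, and I read the bullets as applying to the study drug.

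**Patient with a Grade 2 reaction that recurs after resumption**

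1. First reaction: infusion stopped, then resumed at 50% of the previous rate. Only the Grade 2 bullet speaks to this step.
2. The reaction recurs at that rate. Current infusion: the Grade 2 bullet stops it, and so does the re-treatment bullet. They agree.
3. Later infusions: the Grade 2 bullet says to premedicate them, so they take place. The re-treatment bullet says there are none. They disagree.
4. Can Section 5.2.3 decide? Its condition is that the patient may continue under Appendix 5, which is the question left open at step 3. The reference is circular.

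**Where the difference shows in the analysis**

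- SAP 9.2.4 summarises cycles started and time on treatment, and tabulates discontinuation with its reason. Each depends on step 3.
- SAP Appendix 3, Table 3 censors PFS at the last tumour assessment when treatment stops for toxicity, so a permanent stop can also change how a patient enters PFS.
- Part 2 plans approximately 20 patients, so each affected Part 2 patient moves a discontinuation percentage by 1/20 = 5 percentage points.

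**Where it does not show**

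- *Cycle 1 infusion.* Both instructions stop the current infusion (step 2), so the Cycle 1 dose received is the same under either.
- *Evaluability.* SAP 6.8 counts less than 80% of the planned Cycle 1 dose as a major deviation only when the shortfall is not due to treatment-related toxicity. A shortfall from a treatment-related reaction does not make the patient non-evaluable under that rule.
- *DLTs.* Protocol 3.3 confines DLTs to the first 21-day cycle and excludes even Grade 3 or higher infusion and allergic reactions. The event here is Grade 2, and the disagreement concerns later cycles.

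**Lesser overlap: Grade 1 chills and fever**

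The general sentence interrupts the infusion and restarts it at half rate. The Grade 1 bullet monitors, and stops only on worsening. A Grade 1 reaction that presents as chills and fever fits both. Whether the lower rate then carries to later infusions depends on one more step: the re-treatment bullet applies only if the rate was lowered for an allergic reaction or cytokine release syndrome. If the event is classed that way, a full later infusion takes 60/0.5 = 120 minutes, against the 60 ± 5 minutes in Section 5.2.3. If it is not, nothing carries over.

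**The case against.** The strongest reply is that the appendix can be read without contradiction.

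- The premedication sentence also closes the Grade 1 bullet, so it may be a standing instruction for any Grade 1 or 2 reaction and not the consequence of recurrence. The Grade 2 bullet would then say only to stop the infusion, and the re-treatment bullet would add that dosing ends. The condition in Section 5.2.3 fits this reading.
- Alternatively, the re-treatment bullet may concern only reactions at later infusions, as its heading suggests. Recurrence within the same infusion would then be left to the Grade 2 bullet.

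Both readings are plausible, but neither is written down. The premedication sentence follows the recurrence clause with no exception, and the re-treatment bullet is not limited to later infusions. The two readings also lead to opposite outcomes for the same patient: the first ends dosing and the second allows it. Their existence explains how the text may have arisen, but does not tell a site what to do.

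On the lesser overlap, it is fair to say that the chills-and-fever sentence is triggered by symptoms and the Grade 1 bullet by a graded diagnosis. That makes it the weaker of the two. It remains unclear which governs when both triggers are met.

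**Conclusion.** The conflict stands on the plain wording: one event, two outcomes for later dosing, and no text that ranks them. For any patient whose Grade 2 reaction recurs at the halved rate, further treatment depends on which bullet the site follows. How many patients that is cannot be said, since the documents give no reaction rate. The effect is limited to re-exposure risk, cycles received, and discontinuation and related exposure summaries.

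A reader might go further and infer that the ambiguity changes who completes Cycle 1, who counts toward the MTD, or the mCRM estimate. The documents do not support that: both bullets stop the current infusion, SAP 6.8 exempts shortfalls due to treatment-related toxicity, and the DLT definition covers Cycle 1 only. A reader might also infer that every patient with Grade 1 chills and fever could end up on half rate for all later infusions. That holds only if the event is classed as an allergic reaction or cytokine release syndrome.

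The conclusion assumes that a recurrence after resumption counts as a second reaction at the lower rate, which is its ordinary meaning and is nowhere excluded.

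**What to change.** Reconcile two pairs of instructions in Appendix 5 so that each situation has one outcome:

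1. The Grade 2 bullet with the re-treatment bullet. State whether a recurrence within the same infusion counts as the second reaction, and whether the premedication sentence applies to a patient whose reaction has recurred.
2. The chills-and-fever sentence with the Grade 1 bullet. State which governs when both fit, and whether a rate lowered under the general sentence carries to later infusions.

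Then align the cross-reference in Section 5.2.3. Which rule to adopt is a clinical decision for the sponsor, and this review takes no position on it. The cost is a protocol clarification; the sample size, endpoints and SAP methods need no change.
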